14 STUDY MONITORING

Each site will provide regular status reports to CORE. Status reports will include:

- The number of participants screened, enrolled, and randomized (i.e. assigned a study ID number), discontinued and completed.
- Details of all protocol deviations, adverse events, device malfunctions.
- Reports of unintended events.

CORE will collate the site updates and provide 2-weekly status reports to the study sponsor.

Study monitoring visits may be conducted by the sponsor, or sponsor's designate, throughout the study and will be scheduled in conjunction with the Principal Investigator at each site. In addition study records may be inspected by the sponsor, the sponsor's designate, the relevant research ethics review board, and by regulatory authorities in Canada and the United States, namely Health Canada and the United States Food and Drug Administration (FDA); however, they will not be permitted to take away any records containing identifiable personal information.

Study data review and data monitoring will be conducted by CORE personnel. To improve data integrity, data entry will be conducted by two people and the entries will be compared. Data

queries will be reported to the site within 5 working days of receipt of initial data. A response resolving the query will be expected from the site within 5 working days of receipt of the query.

All adverse events and protocol deviations will be reviewed by the site Principal Investigator and CORE. All serious adverse events and major protocol deviations will be reviewed by the site Principal Investigator and CORE's Head of Clinical Research and/ or CORE's Principal Investigator.

15 STUDY MANAGEMENT

15.1 STATEMENT OF COMPLIANCE

This clinical study is designed to be in compliance with the ethical principles in the Declaration of Helsinki, with the ICH guidelines for Good Clinical Practice (GCP), with the University of Waterloo's Guidelines for Research with Human Participants and with the Tri-Council Policy Statement: Ethical Conduct for Research Involving Humans, 2nd Edition.

- Declaration of Helsinki
- ICH E6 - International Conference on Harmonisation; Good Clinical Practice
- <http://iris.uwaterloo.ca/ethics/human/guidelines/index.htm>
- <http://iris.uwaterloo.ca/ethics/human/ethicsReview/UWStatement.htm>
- <http://www.pre.ethics.gc.ca/eng/policy-politique/initiatives/tcps2-eptc2/Default/>

15.2 ETHICS REVIEW

This protocol will be submitted to and reviewed through the Office of Research Ethics (ORE) at the University of Waterloo for study site H (CORE), the Health Research Ethics Board of Alberta – Clinical Trials Committee (HREBA-CTC) for study site G and the Sterling Institutional Review Board (IRB) for all other clinical study sites. Notification of ethics clearance of the application is required prior to the commencement of the study the respective provinces and sites.

15.3 CLINICAL TRIAL REGISTRATION

CooperVision will register this study with clinicaltrials.gov and maintain the information.

15.4 PROTOCOL DEVIATIONS

Protocol deviations are unanticipated or unintentional changes to a study after it has received prior sponsor approval and ethics clearance. Protocol deviations can be major or minor.

15.4.1 MAJOR PROTOCOL DEVIATIONS

Major protocol deviations may impact the research protocol, information consent document or other study materials, usually cannot be anticipated ahead of time and are often necessary to ensure the safety and welfare of the participants.

The following are examples of major protocol deviations that require reporting to research ethics review boards::

- Changes in procedures initiated to eliminate immediate risks/hazards to participants;
- Enrollment of participants outside the protocol inclusion/exclusion criteria whether agreed to or not by the sponsor;
- Medication / device / intervention errors (i.e. incorrect drug or dosage of drug / incorrect contact lens(es) dispensed / incorrect care system dispensed);
- Inadvertent deviation in specific research intervention procedures or timing of the research intervention which could impact upon the safety or efficacy of the study-related intervention or upon the experimental design;
- Information consent documentation violations: no documentation of informed consent; incorrect version of, or incomplete, informed consent documentation used.

15.4.2 MINOR PROTOCOL DEVIATIONS

Protocol deviations caused by or which originate with research participants are considered minor, and normally are not reported to the research ethics review board unless these result in increased risk to the participant(s). The following are examples of protocol deviations that are considered minor and do not require reporting to the research ethics review board::

- Logistical or administrative aspects of the study (e.g., study participant missed appointment, change in appointment date);
- Inadvertent deviation in specific research intervention procedures or timing of the research intervention which would not impact upon the safety or efficacy of the study-related intervention or upon the experimental design (i.e., missing a measurement during a session that is not considered critical for the study).

15.4.3 REPORTING AND DOCUMENTING PROTOCOL DEVIATIONS

Protocol deviations must be reported to the site Principal Investigator and CORE's contact below. CORE will inform the sponsor within 7 days of any major protocol deviations that occurred during the study. Major protocol deviations must be reported by the site Principal

Investigator, overseen by CORE's contact, to the research ethics review board via the IRB specified method (by fax, mail/ delivery, phone or email) within 7 days of the deviation occurring (or its discovery) unless otherwise specified by the IRB.

All protocol deviations (major and minor) occurring during the study will be documented and included in the final report.

[REDACTED]

15.5 PREMATURE TERMINATION OF THE STUDY

The sponsor, CORE or the relevant research ethics review board may terminate the study at any time for any reason.

15.6 STUDY PARTICIPANT RECORDS

Study participant records will be completed to comply with GCP guidelines. Records will contain:

- Unique study acronym and/or code;
- Participant ID;
- Date enrolled;
- Confirmation by investigator that participant met eligibility criteria;
- Confirmation that participant received a signed and dated copy of informed consent;
- Exit date;
- Investigator's signature confirming study exit.

An enrolment log will be maintained which will list all participants who attended for a screening visit.

15.7 RETENTION OF STUDY RECORDS AND DATA

When the study has been completed, all sites will send the original study product accountability and dispensing logs, and the original consent documentation and enrolment logs to CORE. Each site should retain the original study data collection forms documentation for one year following the close of the database in case data queries arise during the analysis and report writing stages. CORE may request that these originals be sent to them for storage.

Records and data from this study will be retained at CORE for a minimum of 25 years. Details regarding storage procedures are given in CORE SOP014 Clinical data management.

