5.1.3 MASKING

Participants will be masked to the lens type they are wearing during the study. Foils will not be visible to participants when the lenses are removed from the blister packs and information specifying which lens is being worn will not be shared with the participant.

It is not possible for the study investigators to be masked because of the need to follow the specific lens fitting guide during the lens prescription optimization visit (visits 1-1 and 2-1).

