12 STATISTICAL ANALYSIS AND DATA MANAGEMENT

12.1 STATISTICAL ANALYSIS

All data will be analyzed by CORE at the University of Waterloo. Unmasked data analysis will be conducted using Statistica 10, Statsoft or other suitable software. Descriptive statistics will be provided on demographic data (age, gender, refractive error distribution, etc.). Table 7 lists the primary and other outcome variables and anticipated statistical procedures.

Visual acuity results will be converted to LogMAR for analysis purposes.

Comparisons will be made between the study lenses for the variables measured at the 1 month visits. Additionally the subjective ratings completed on days 7, 14 and 28 of each phase will be compared. A binomial test will be used to analyze the results for the count data of subjective preferences and experience responses. Where relevant, the number of “neither agree or disagree” responses will be evenly distributed to the two options on the basis they would be equally likely to choose either.

Because of the phenomenon of binocular summation, binocular visual acuity will be analysed, not right eye data. For other variables, such as lens fit, the right eye data will be reported and compared.

Where appropriate, such as for lens orientation, data may be presented as both mean and as counts by 'bucket' groups.

Table 7: Statistical procedures

Variable	Analysis	Statistical test
Ratings: Likert & Preference	Comparison between study days and/or between contact lenses per time point.	Freidman ANOVA Wilcoxon matched pairs test
Ratings: numerical ratings Biomicroscopy	Comparison between study days and/or between contact lenses per time point.	Freidman ANOVA Wilcoxon matched pairs test RMANOVA
Demographics Lens fit variables	Descriptive stats	One or more: mean, median*, mode, standard deviation, minimum, maximum, frequency count

* For non-parametric data only

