12.2 DATA MANAGEMENT

Data will be collected and written on paper forms which will be provided to each site by CORE. Each external site will email scanned forms to a designated person at CORE who will file the forms into pre-assigned binders and pass these binders to the data entry team. Data will be entered into a REDCap database developed and tested specifically for this study and accessible only to trained, authorised users. A data management plan will be developed to describe the data handling in more detail, including the personnel involved.

Data from this study will be retained by CORE for a minimum of 25 years on a password-protected server. After 25 years, data will be disposed of in accordance with the guidelines laid out by the University of Waterloo. More details regarding storage procedures are provided in section 15.7 and also in CORE SOP014 Clinical data management.

At the completion of the study CORE will provide a copy of the study data to the sponsor when requested. Data will typically be sent using a secure file share system operated by the University of Waterloo called Sendit which uses 128bit (or 256bit) SSL encryption. This system provides a secure way to transfer files when email is not appropriate, whether because of file size, file type or concerns over security. Sendit includes features such as password protection, a restricted

time period for download, IP logging and email notification of download. Files may be encrypted prior to transmission at the request of the sponsor. Using this method means that data files are only stored on University of Waterloo servers during the transfer.

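### The analysis is planned unmasked, and late data queries and decisions on out-of-window data can fall within it; coding the lenses A/B until these are settled is a cheap improvement

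*Combined protocol and SAP*

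**What the plan says.** On masking, Section 12.1 reads "Unmasked data analysis will be conducted using Statistica 10, Statsoft or other suitable software". It also names the analyst: "All data will be analyzed by CORE at the University of Waterloo". Under Section 5.1.3 participants are masked to lens type, but "It is not possible for the study investigators to be masked".

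On data review, Section 14 says "Study data review and data monitoring will be conducted by CORE personnel". It provides that "data entry will be conducted by two people and the entries will be compared", and that data "queries will be reported to the site within 5 working days of receipt of initial data", with a site response expected within a further 5 working days.

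On late queries, Section 15.7 asks each site to hold its original data collection forms "for one year following the close of the database in case data queries arise during the analysis and report writing stages". CORE may also ask for those originals.

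On the analysis population, Section 5.4 treats visits outside their windows as protocol deviations. It leaves to the end of the study the question of whether data from deviations are suitable for analysis. It does not say whether that decision comes before or after the lenses are compared.

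On further controls, Section 12.2 says "A data management plan will be developed to describe the data handling in more detail". Sections 12.2 and 15.7 also refer to CORE SOP014. Neither the plan nor the SOP is part of the documents.

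**The concern.** Two kinds of decision can alter the data behind the primary comparison late in the study: resolving a query, and judging whether out-of-window data are usable. Both are best made without knowing which lens a value belongs to or which way the comparison is going. Otherwise a value that runs against expectation may be looked at harder than one that agrees with it. An expected direction exists here, because Section 2 reports that an earlier sponsor study found the non-multifocal lens of the sponsor's family easier to insert than the competitor's.

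As written, nothing in the protocol separates these decisions from knowledge of the lens. One organisation reviews the data and analyses them unmasked. The protocol does not state when lens identity is joined to the ratings, or how a change after database close would be approved and recorded. What is at stake is the credibility of the Day 28 handling comparison against a competitor's product, and possibly a small bias in it.

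**Working it through.** This is mainly a matter of setting the sections side by side. The arithmetic gives only a sense of scale.

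**Who knows what, and when**

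- Participants are masked (5.1.3). They record the primary rating themselves at home, on a 0 to 10 integer scale (5.4.6), on a paper form returned and reviewed at visits 1-2 and 2-2 (5.4).
- Site investigators know the lens (5.1.3). No section says that they see results.
- CORE reviews the data (14) and analyses them unmasked (12.1). During analysis its staff can know both the lens and the emerging comparison.
- Routine queries are prompt: 5 working days to raise and 5 to answer (14). The queries foreseen in 15.7 come later, after close and during analysis or report writing, so they overlap with the unmasked analysis.
- The decision on out-of-window data comes at the end of the study (5.4), with no stated order relative to the lens comparison.

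So the overlap in time and in organisation follows from the text. An actual change to a rating does not.

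**The plan's own figure**

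Inputs from Section 5.2.1: difference 0.7, SD 1.7, two-sided alpha 0.05, power 80%. Reading 1.7 as the SD of the within-person difference, the paired t-test (noncentral t) gives power 0.798 at n = 48 and 0.806 at n = 49. The stated 49 is reproduced. The present point does not alter it.

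**Scale**

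- Standard error of the mean difference: 1.7/√49 = 0.243.
- Smallest significant difference: t(0.975, 48 df) × 0.243 ≈ 0.49.
- A net one-directional change of P rating points, summed over participants, moves the mean difference by P/49.

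| Net points P (assumed) | Shift P/49 | In standard errors | Share of 0.7 |
|---|---|---|---|
| 1 | 0.020 | 0.08 | 3% |
| 5 | 0.102 | 0.42 | 15% |
| 10 | 0.204 | 0.84 | 29% |

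The values of P are assumptions, since the documents give no basis for choosing one. A few small corrections would matter little. Only a substantial net movement in one direction would matter.

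**The case against.** The strongest reply is that Section 15.7 is a record-retention sentence. It says how long to keep originals in case a query arises. It does not predict queries, reopen the database or permit a rating to be altered, and a query can end with the value confirmed. Keeping the originals is itself a safeguard. The primary value is a masked participant's own entry, held on paper at the site and as a scan at CORE (12.2), so an altered value would disagree with both. Double entry leaves few genuine discrepancies. Late queries may also concern dates, lens parameters or adverse events rather than ratings. Lock and change rules commonly sit in a data management plan or SOP, and Section 15.1 commits the study to GCP.

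Most of this stands, and it rules out some tempting stronger readings:

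- A reader might infer that ratings are expected to be questioned and changed after close. The documents are silent on such changes; they do not plan or allow them.
- A reader might infer that those answering queries know the result. Sites know the lens, but nothing says that results are shared with them.
- A reader might want an inflated false-positive rate, computed by neutralising the most unfavourable differences. That would describe overwriting source data, not resolving queries, so it is no estimate of bias here.

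What the reply does not answer is the explicit statement in 12.1. Retained forms protect against a wrong value. They do not stop queries from being raised selectively, and they do not bear on which out-of-window data are kept. Nothing in the documents suggests that the unseen plan or SOP would reverse the stated choice of an unmasked analysis.

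**Conclusion.** The point holds in a limited form and is minor: a cheap improvement, not a defect that threatens the trial. The protocol plans an unmasked analysis by the organisation that also reviews the data. It provides for queries while that analysis is under way, and it leaves the judgement on out-of-window data to the end of the study. CORE staff could therefore make these decisions knowing the lens and the emerging comparison.

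No bias can be estimated, because the documents give no number or direction of late changes. The shifts shown rest on 49 completers, on 1.7 being the SD of the paired difference, and on assumed net changes.

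Two qualifications apply. The absence of a rule for post-close changes can be asserted only for these documents, since the data management plan or SOP014 may contain one; taken alone, that part is missing detail. Section 5.4 also words the out-of-window rule for visits and data from deviations. Section 6 monitors the timing of ratings, but neither section says outright when a mistimed Day 28 rating would be dropped.

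**What to change.** 1. **Section 12.1 (main change).** Replace the statement that the analysis is unmasked. Analyse the primary Day 28 ratings on a dataset in which the lenses carry neutral codes A and B. The Database Administrator, who generates the randomization schedule (5.1.2), releases the key only when the database is closed, all Day 28 queries are resolved and the analysis population, including decisions on out-of-window data, is fixed. Keep lens parameters out of that dataset: Table 1 shows that axis steps and ADD designations differ between the lenses and could reveal the code. Those making these decisions should not hold the schedule, which 5.1.2 also gives to research assistants at each site.

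2. **Section 15.7 (supporting sentence), or a cross-reference to the data management plan.** Allow a post-close change only where the database differs from the original form, and log it with old and new values. If a Day 28 rating is affected, report the primary result with and without the change. If the plan or SOP014 already says this, a cross-reference is enough.

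The cost is one recoded variable in the data export, a few sentences of text and a short delay before lens names appear in the output. No visits or participants are added, and the sample size is unchanged.

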16 REPORT

A report will be sent to the sponsor by CORE according to terms described in the study contract.
